## **8.2.4 Analysis Populations**

### **8.2.4.1 Efficacy Analysis Populations**

The Full Analysis Set (FAS) population will serve as the primary population for the analysis of efficacy data in this study. The FAS population for a given endpoint consists of all randomized subjects who:

- receive at least one dose of study treatment,
- have both 1) a baseline measurement for the analysis endpoint and 2) at least one within-analysis-window ( $\pm 6$  weeks) post-dose, post-randomization observation for the analysis endpoint, and
- are PET positive.

All available observations from the initial 104-week trial will be included in the relevant model-based FAS analyses. Observations from the long term trial will be included according to the principles outlined above, with the following additional requirement: the subject must have taken at least one dose of study medication within the 28 days preceding the 104-week visit and within the 28 days following the 104-week visit.

The Modified Full Analysis Set (MFAS) population will be utilized for sensitivity analyses and is defined identically to the FAS population with one exception: patients will only be required to have either 1) a baseline measurement for the analysis endpoint or 2) at least one within-analysis-window ( $\pm 6$  weeks) post-dose, post-randomization observation for the analysis endpoint, but not necessarily both.

The MFAS population will be utilized to conduct sensitivity analyses in this study for the primary endpoint (CDR-SB 30-Month CFB).

Though no Per-Protocol analyses are planned, a list of protocol violations/violators will be maintained. The final determination on protocol violations will be made prior to the final unblinding of the database and will be documented in a separate memo.

Subjects will be included in the treatment group to which they are randomized for the analysis of efficacy data using the FAS population.

### **8.2.5 Safety Analysis Populations**

The All Subjects as Treated (ASaT) population will be used for the analysis of safety data in this study. The ASaT population consists of all randomized subjects who received at least one dose of study treatment. Subjects will be included in the treatment group corresponding to the study treatment they actually received for the analysis of safety data using the ASaT population. For most subjects this will be the treatment group to which they are randomized. Subjects who take incorrect study treatment for the entire treatment period will be included in the treatment group corresponding to the study treatment actually received.

At least one laboratory or vital sign measurement obtained subsequent to at least one dose of study treatment is required for inclusion in the analysis of each specific parameter. To assess change from baseline, a baseline measurement is also required.

### **8.2.6 Statistical Methods**

Statistical testing and inference for safety analyses are described in Section 8.2.8. The final analysis is expected to be carried out using SAS v9.3.

### **8.2.7 Statistical Methods for Efficacy Analyses**

#### **8.2.7.1 Primary Efficacy Analysis**

The primary efficacy endpoint is the change from Baseline (CFB) in CDR-SB score at Week 130. Basic summary statistics (means and standard deviations, as observed), will be calculated.

A delayed start design will be used to support the potential disease modifying effect of MK-8931 by comparing the 40 mg/40 mg arm to the Pbo/40 mg arm. However, due to increased variance and anticipated dropout rate over time, the study is not powered to demonstrate significance on these endpoints, even if significance was demonstrated at 24 months in the initial study.

The 12 mg/12 mg arm will be compared to the Pbo/40 mg arm in a similar fashion.

All available data from the initial 104-week trial will be utilized in the analyses, even that from subjects who do not continue into long term trial. It is possible that the 40 mg dose may be dropped for reasons due to safety, in which case all subjects would receive 12 mg. The primary comparison in this case would be between the 12 mg / 12 mg arm and the Pbo / 12 mg arm (with any subjects receiving 40 mg excluded from the analysis).

A longitudinal ANCOVA model will be used on the change scores, with time treated as a categorical variable so as not to impose any restriction on the trajectory of the means over time. The analysis model includes treatment, time, the time-by-treatment interaction, APOE4 genotype (APOE4 positive, APOE4 negative), gender, geographic region, and the use of acetylcholinesterase inhibitors at screening (Use, Do Not Use) as categorical terms, with age and baseline MMSE score as continuous covariates. The baseline value of the dependent

variable, as well as the baseline-by-time interaction term will also be included. Model-based estimates of the mean change scores and the mean treatment difference on the change scores will be provided, along with the corresponding confidence intervals and p-values for the mean treatment differences. An unstructured covariance matrix will be used to model the correlation among repeated measurements.

Three supportive analyses will be conducted on the primary efficacy endpoint. These analyses will be conducted to assess the effect of 1) missing data using a pattern-mixture model “tipping-point” approach, which is intended to provide a measure of robustness in the (unobservable) event that a larger-than-expected proportion of the missing data be missing-not-at-random (MNAR) 2) the use of off-regimen data after the subject has permanently discontinued trial medication or after the subject has initiated AChEIs and 3) analysis using the cLDA model on the MFAS population.

For the first sensitivity analyses (tipping-point), the model-based estimates of the mean treatment difference on the change scores, along with the corresponding confidence intervals and p-values will be provided for a range of  $c$  values which have been subtracted from the values imputed for the active arms (see Section 8.2.7.5 for more details). Of specific interest is the smallest  $c$  value that, for a given endpoint, transforms a “statistically significant” result to a “non-statistically significant” result (per the pre-defined  $\alpha$ -level used in the initial 104-week trial).

For the second sensitivity analysis (excluding observations obtained after study medication discontinuation or after the initiation of AChEIs), the model-based estimates of the mean treatment difference on the change scores, along with the corresponding confidence intervals and p-values will be provided.

For the third sensitivity analysis (cLDA model on the MFAS population), the analysis of the primary efficacy endpoint will be conducted using a constrained longitudinal data analysis (cLDA) method proposed by Liang and Zeger [28]. This model assumes a common mean across treatment groups at baseline and a different mean for each treatment at each of the post-baseline time points. The response vector consists of baseline and the values observed at each post-baseline time point. The model-based estimates of the mean treatment difference on the change scores, along with the corresponding confidence intervals and p-values will be provided as obtained using the cLDA model, with all of the same covariates that were included in the primary model (now excluding the terms for baseline and baseline-by-time interaction). An unstructured covariance model will be used.

Table 6 Analysis Strategy for Primary Endpoints

Endpoint/Variable (Description, Time Point)	Primary vs. Supportive Approach	Statistical Method	Analysis Population	Missing Data Approach
Primary Endpoint				
CFB in CDR-SB scores at 130 Weeks	P	Longitudinal ANCOVA	FAS	Model-based
	S	Longitudinal ANCOVA	FAS	Pattern-Mixture Model (Tipping Point)
	S	Longitudinal ANCOVA (Exclude data collected after the introduction of AChEIs and/or study medication discontinuation)	FAS	Model-based
	S	cLDA	MFAS	Model-Based
AChEIs= acetylcholinesterase Inhibitors; CFB=Change from baseline.				

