### **5.1.2 Subject Inclusion Criteria**

In order to be eligible for participation in this trial, the subject must:

1. Have tolerated study medication and completed the initial 104-week trial. Subjects who did not complete the initial 104-weeks of treatment but continued with and completed scheduled visits may be permitted to continue in the long term extension at the discretion of the Sponsor. Subjects who repeatedly deviate from protocol requirements will not be permitted to continue in this extension. In addition, subjects who are less than 75% compliant with trial medication during the initial 104-week trial will not be permitted to continue in the long term extension, except in special circumstances, which require Sponsor approval (or, where required locally, approval of the investigator rather than the Sponsor).
2. Have a trial partner who is reliable and competent. The trial partner must have a close relationship with the subject, have face to face contact at least 3 days/week for a minimum of 6 waking hours/week (or more, based on local requirements), be willing to accompany the subject to all trial visits, and be willing to monitor compliance of the administration of the trial medication. The trial partner should understand the nature of the trial and adhere to trial requirements (e.g. dose, visit scheduled and evaluations). It is recommended that the trial partner accompany the subject to all trial visits.
3. Sign (or legal representative signature) the informed consent in accordance with local requirements, after the scope and nature of the trial have been explained.
4. Agree to inform their general practitioner of their participation in this study.

**Note:** PI will follow up with subject to ensure compliance and document notification of the general practitioner in subjects medical records.

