## 5.2 Trial Treatments

The treatments to be used in this trial are outlined below in [Table 2](#).

Table 2 Trial Treatments

Drug	Dose/Potency	Dose Frequency	Route of Administration	Regimen/Treatment Period	Use
MK-8931	12 mg tablet	Once daily	Oral	Up to 260 weeks	Investigational
MK-8931	40 mg tablet	Once daily	Oral	Up to 260 weeks	Investigational

Subjects who received the 12 mg or 40 mg dose in the initial 104-week trial will continue to receive the same dose in this long term trial. Subjects who received placebo during the initial 104-week trial will receive the 40 mg dose during this long term trial.

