#### **5.2.2 Timing of Dose Administration**

The trial medication should be administered by the subject, by the subject’s trial partner, or by a caregiver. Each subject should take one tablet at approximately the same time each day without regard to food. For each treatment group, one tablet equals one dose of trial medication as summarized below:

- 12/12 group: MK-8931 12 mg (one tablet)
- 40/40 and placebo/40 groups: MK-8931 40 mg (one tablet)

If a subject misses a dose, the subject may take the dose later in the day and should continue with the regular dosing schedule by taking the next dose at the usual time the next day. Any changes in dosing schedule should be noted by the subject or subject’s trial partner and recorded by the site at the next visit. Subjects should not take more than one dose on the same calendar day.

With the exceptions of any subjects enrolled to a dose that is dropped for reasons of safety or tolerability, there will be no adjustments to the dose of any subject in the trial.

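### If 40 mg is dropped after some placebo subjects have started it, the exclusion rule read literally deletes those subjects whole, Part I data included, from the control arm only

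*Combined protocol and SAP*

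**What the plan says.** Section 8.2.7.1 (Primary Efficacy Analysis) sets a fallback in case 40 mg is dropped for safety: "The primary comparison in this case would be between the 12 mg / 12 mg arm and the Pbo / 12 mg arm". A parenthesis attached to that sentence adds an exclusion: "with any subjects receiving 40 mg excluded from the analysis". Just before that, the same section sets a rule that also covers people who never enter the extension: "All available data from the initial 104-week trial will be utilized in the analyses, even that from subjects who do not continue". Section 8.2.4.1 analyses efficacy by randomised group.

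Section 5.2 fixes who is on 40 mg: "Subjects who received placebo during the initial 104-week trial will receive the 40 mg dose during this long term trial". It also says: "Subjects who received the 12 mg or 40 mg dose in the initial 104-week trial will continue to receive the same dose". A subject on 12 mg therefore does not meet 40 mg by design.

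Section 5.2.2 foresees a drop while subjects are already on the dose, since its bar on dose adjustment begins: "With the exceptions of any subjects enrolled to a dose that is dropped for reasons of safety or tolerability".

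Entry to the extension is selective. Section 5.1.2 asks subjects to "Have tolerated study medication and completed the initial 104-week trial", with an exception at the sponsor's discretion for those who stopped treatment but kept attending visits. Section 5.1.3 excludes subjects whom the investigator has diagnosed with AD dementia.

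**The concern.** The exclusion is written for subjects, not for observations. A placebo subject who has begun 40 mg in the extension is a subject receiving 40 mg, so the literal rule removes that person's placebo record from the initial 104 weeks as well. Placebo subjects who never entered the extension keep theirs.

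Removal then depends on something that happens after randomisation, in one of the two compared arms. The placebo subjects removed come from those who entered the extension, mostly completers without investigator-diagnosed AD dementia. Their counterparts in the 12/12 arm all stay. What remains of the control arm holds a larger share of dropouts and progressors. If those subjects decline faster, control looks worse than it should and 12 mg looks better.

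The longitudinal model does not repair this. A likelihood-based model can recover from missing later visits by using a subject's earlier ones. Here the earlier visits are deleted too, so the control means are already shifted within the initial trial.

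**Working it through.** **Inputs from the documents.** 450 randomised per arm, 25% dropout at Week 104, 37% at Week 130, and 90% of completers continuing (Section 8.2.11.1.2 and Table 9); about 912 entrants in all (Section 1.0).

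**Inputs not in the documents.** The share f of placebo entrants already on 40 mg when the dose is dropped, and the gap g in CDR-SB change between non-entrants and entrants. Both are assumptions, shown as ranges.

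**Step 1: the plan's own figure.** 450 × 0.75 × 0.90 = 303.75, or 304 per arm, and 304 × 3 = 912. The stated enrolment is reproduced. Entrants are 303.75/450 = 67.5% of an arm and non-entrants 32.5%.

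**Step 2: what the rule removes.**
- Placebo subjects removed = 303.75 × f. Removed from 12/12 = 0.
- Entrant share of the remaining control arm: s(f) = 0.675(1 − f) / [0.675(1 − f) + 0.325]. At f = 0.5 this is 0.3375/0.6625 = 0.509. At f = 0.75 it is 0.16875/0.49375 = 0.342.
- Control subjects with Week 130 data = 450 × 0.63 × (1 − f).
- Shift in the control mean = (0.675 − s(f)) × g.

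| f | Removed from placebo | Entrant share, control | Entrant share, 12/12 | Control n, Week 130 | Shift, g = 1 | Shift, g = 2 |
|---|---|---|---|---|---|---|
| 0 | 0 | 67.5% | 67.5% | 284 | 0 | 0 |
| 0.25 | 76 | 60.9% | 67.5% | 213 | 0.07 | 0.13 |
| 0.50 | 152 (34% of 450) | 50.9% | 67.5% | 142 | 0.17 | 0.33 |
| 0.75 | 228 (51% of 450) | 34.2% | 67.5% | 71 | 0.33 | 0.67 |

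**Step 3: does the shift survive a repeated-measures model?** A simulation with no true treatment difference (1,500 replicates per setting) fitted a likelihood-based repeated-measures model. It assumed visits at Weeks 52, 78, 104 and 130, a correlation of 0.85 per visit step, dropout depending on the last observed score, and switched subjects being a random subset of placebo entrants. None of these comes from the documents. Two positive gaps at Week 104 were used, about 1.0 and about 1.8 points. The nominal false-win rate for 12 mg is 0.02495/2 = 1.25%, taking alpha as two-sided.

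| f | Bias favouring 12 mg, gap 1.0 (1.8) | False-win rate, gap 1.0 (1.8) |
|---|---|---|
| 0 | 0.00 (0.00) | 1.3% (1.3%) |
| 0.25 | 0.07 (0.12) | 2.6% (4.6%) |
| 0.50 | 0.17 (0.33) | 5.3% (18.5%) |
| 0.75 | 0.38 (0.70) | 15.3% (50.3%) |

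With a gap of zero the bias stayed within 0.01 at every f. The model did not remove the shift: at f = 0.5 and a gap of 1.0, bias was 0.19 at Week 104 and 0.17 at Week 130.

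**Step 4: the same simulation with control data kept up to the first 40 mg dose.** Bias at Week 130 lay between −0.014 and +0.010 in every setting and the false-win rate between 0.9% and 1.7%. At positive gaps the empirical standard error was about 0.22 at f = 0, 0.23 at f = 0.5 and 0.27 at f = 0.75. Under literal deletion it was about 0.25 at f = 0.5 and 0.30 to 0.31 at f = 0.75.

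**The case against.** The strongest reply is that the parenthesis refers only to the arm randomised to 40 mg. The text supposes that after a drop everyone receives 12 mg, so subjects randomised to 40 mg would be on 12 mg too, and saying that this third arm leaves a model with a treatment factor and a common covariance matrix has a purpose. The neighbouring all-data sentence and the as-randomised rule favour this reading, under which no placebo subject loses initial-trial data. It may well be the intent. But the words cover any subject receiving 40 mg, and the comparison already names only the two other arms. The arm-level reading also leaves open what happens to a placebo subject's observations after a first 40 mg dose. Two programmers could build different primary analyses.

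The point is also doubly contingent: 40 mg must be dropped, and after some placebo subjects have started it. That stands. So does the limit on the stakes: the extension has no formal hypotheses and describes itself as underpowered. The comparison would still supply the estimate for a primary objective, with confidence intervals and p-values.

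The 304 entrants rest on dropout and continuation rates alone. The plan shows no separate allowance for excluding subjects with AD dementia, so the true number could be lower.

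**Conclusion.** The rule is wrong as written, within a contingency that the plan itself provides for. Read literally it deletes valid placebo data from one arm of the fallback comparison and contradicts the all-data and as-randomised rules. The head counts follow from the plan's rates once f is assumed: at f = 0.5, about 152 of 450 placebo subjects are deleted. The shifts (0.17 to 0.33 points at f = 0.5, 0.33 to 0.67 at f = 0.75) are illustrative, because neither f nor the gap is in the documents.

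Three stronger readings that a reader might infer are not supported.
- That everyone removed is by definition a completer without AD dementia. Sections 4.2.1.2 and 5.1.2 admit some subjects who stopped treatment, and the dementia criterion rests on the investigator's diagnosis.
- That the result is certain to favour 12 mg. The direction needs non-entrants to decline faster, and some non-entrants are simply completers who choose not to continue.
- That the bias matches the effect the trial was designed to detect. Table 9 states no effect size and concerns 40/40 against Pbo/40. Back-solving its 73.9% power with 450 × 0.63 = 283.5 per arm gives (2.24 + 0.64) × SD × √(2/283.5), about 0.69 for an SD of 2.85 (3.05 × √(1 − 0.359²)) and 0.74 for an SD of 3.05. That is not a benchmark for the 12 mg contrast.

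**What to change.** Reword the parenthesis in Section 8.2.7.1. If 40 mg is dropped, exclude the arm randomised to 40 mg. Keep every placebo-randomised subject with all observations up to the first 40 mg dose, and exclude only observations after that dose. Fit the same longitudinal model, so that the Week 130 Pbo/12 mean is informed by subjects who go directly from placebo to 12 mg together with all placebo data from the initial trial. Settle the wording before the sponsor is unblinded at the end of the initial trial.

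The cost is one sentence and a little programming to censor at the first 40 mg dose. Fewer Week 130 control observations are available than if data after 40 mg were used. As f approaches 1, few or no direct switchers remain and the Week 130 Pbo/12 mean can hardly be estimated, so the SAP should say what is reported then. The approach also assumes that direct switchers resemble earlier entrants given their observed data. The change concerns the analysis only and implies nothing about dosing.

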##### **4.1.1 Pharmaceutical and Therapeutic Background**

Alzheimer's Disease (AD) is a slowly developing neurodegenerative disease that is the leading cause of dementia world-wide. Currently available treatments for AD are limited, and include acetylcholinesterase inhibitors (e.g., donepezil) and the low affinity N-methyl D-aspartate (NMDA) receptor antagonist (memantine). These medicines modestly improve symptoms but do not alter disease progression. Therefore, novel pharmacological agents that slow or halt the progression of AD are needed.

Alzheimer's Disease is characterized by specific histopathological features including amyloid deposits (plaques), neurofibrillary tangles, and neuronal degeneration. The "amyloid hypothesis" posits that amyloid  $\beta$  ( $A\beta$ ) peptides aggregate into complexes, such as fibrils and plaques, which subsequently trigger the development of tau-related neurofibrillary tangles. These tangles are thought to be the more proximal cause of neuronal degeneration.  $A\beta$  pathology appears to begin years before the onset of AD dementia and is thought at some point to trigger tau pathology, neural degeneration, and the subsequent gradual emergence of clinical symptoms. As amyloid plaques continue to accumulate, tangle pathology spreads to a variety of brain regions, leading to progressive neuronal degeneration, brain atrophy, and cognitive decline. As a result, early intervention to reduce  $A\beta$  accumulation when patients are in the prodromal phase, or even earlier, has gained increasing acceptance as a promising approach to reduce the incidence of AD.

$A\beta$  peptides are produced when amyloid precursor protein (APP) is cleaved by three distinct proteases:  $\alpha$  secretase, BACE1 ( $\beta$  site APP cleaving enzyme 1, also known as  $\beta$ -secretase), and  $\gamma$  secretase. Most APP is processed by  $\alpha$  and  $\gamma$  secretases to generate nonamyloidogenic peptides. However, 5-10% of APP is cleaved by BACE1 and  $\gamma$  secretase to generate pathogenic  $A\beta$  peptides ( $A\beta_{40}$  and  $A\beta_{42}$ ). Deletion of BACE1 in mice eliminates  $A\beta$  in

both the plasma and the brain. Thus, inhibition of BACE1 is a potential therapeutic strategy for slowing or halting progression of AD.

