#### **5.3.2 Allowed Medications**

Medications, supplements, and other substances allowed during the trial include, but are not limited to, those listed in [Table 3](#). Note that the use of any concomitant medication must relate to the documented medical history, prophylaxis, or an adverse event of the subject. **Initiation and change of dose of cholinesterase inhibitors and memantine are allowed in this trial.**

Table 3 Medications, Supplements, and Other Substances Allowed During the Trial

Allowed Medications, Supplements, and Other Substances
Acetylcholinesterase inhibitors (e.g., donepezil, tacrine, rivastigmine, galantamine)
Memantine
Huperzine A
Vitamin E
Herbal supplements from Ginkgo biloba , ginseng, Huperzia serrata (Qian Ceng Ta)
Medical foods/supplements (e.g., Axona ® , Souvenaid ® )
Estrogens and estrogen-like compounds
Antihypertensives
Nonsteroidal anti-inflammatory drugs (NSAIDs)
Cyclooxygenase 2 inhibitors
Neuroleptics
Antidepressants
Carbidopa/levodopa and dopamine agonists
Pregabalin and gabapentin
Rifampicin and St. John's Wort: Topical use, short-term (<2 weeks) oral treatment during the trial, use of oral St. John's Wort <300 mg three times a day during the trial, regardless of duration.
Selective H1 blockers, selective H2 blockers, and topical anti-pruritic treatments for treatment of rash during the trial, as specified in the Rash Guidance Document.

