### 8.2.12 Subgroup Analyses and Effect of Baseline Factors

Subgroup analyses will be conducted on CDR-SB, CCS-3D, ADCS-ADLMCI at Week 130. The consistency of treatment effect across various subgroups will be assessed through the computation of within group summary statistics (model-based and as-observed), along with nominal 95% CIs. Further, model-based between-group treatment differences (or hazard ratios, as appropriate) and the corresponding 95% CIs will be constructed for those comparisons (active/active vs. placebo/active), for which both treatment groups within the subgroup level have at least 75 subjects (roughly 15% of subjects randomized). No formal statistical testing of the treatment by subgroup interactions will be performed. The following subgroups will be examined:

- Gender (Male, Female);
- Age (< 65, ≥ 65 years of age);
- Race (white, black, Asian, other);
- Ethnicity (Hispanic, Not Hispanic);

- Geographic Region (US/Canada, Europe/Australia/New Zealand, Japan, Rest of World);
- APOE Genotype (APOE 4 positive, APOE 4 negative);
- Disease Severity via MMSE at Screening (24-26, 27-30)
- PET/CSF status at Screening (PET+/CSF+, PET+/CSF-, PET+/CSF Unknown, PET-/CSF+)
- CSF evaluation at Screening (CSF evaluated, CSF not evaluated)
- AD Treatment at Screening (use of AChEI or memantine, no use of AChEI or memantine)
- Vitamin E use at Screening (0-400 IU/day, >400 IU/day)

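### The supportive analysis of Week 130 CDR-SB drops data after AChEI initiation but keeps data after memantine initiation, although the extension allows both to be started

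*Combined protocol and SAP*

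**What the plan says.** Section 8.2.7.1 plans three supportive analyses of the primary endpoint, change from baseline in CDR-SB at Week 130. The second is introduced as assessing "the use of off-regimen data after the subject has permanently discontinued trial medication or after the subject has initiated AChEIs". Its operational rule is "excluding observations obtained after study medication discontinuation or after the initiation of AChEIs". Table 6 gives the same rule ("Exclude data collected after the introduction of AChEIs and/or study medication discontinuation"), and its footnote fixes the abbreviation: "AChEIs= acetylcholinesterase Inhibitors; CFB=Change from baseline".

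Elsewhere memantine stands beside the AChEIs:

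- Section 5.3.2, on concomitant medication, states: "Initiation and change of dose of cholinesterase inhibitors and memantine are allowed in this trial".
- Section 4.1.1 names the available treatments as the acetylcholinesterase inhibitors and "the low affinity N-methyl D-aspartate (NMDA) receptor antagonist (memantine", and says of both: "These medicines modestly improve symptoms but do not alter disease progression".
- Section 8.2.12 defines a subgroup as "AD Treatment at Screening (use of AChEI or memantine, no use of AChEI or memantine".

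The primary model in Section 8.2.7.1 adjusts for AChEI use at screening and has no memantine term. Nothing in the plan excludes, censors or adjusts for memantine started after baseline.

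**The concern.** Section 8.2.7.1 compares 40 mg/40 mg with placebo/40 mg at Week 130 to support a disease-modifying effect. A symptomatic drug started along the way can move CDR-SB without changing the disease. If starts differ between arms, part of the observed difference, or of its absence, reflects that drug. The plan acknowledges this for AChEIs by setting aside data collected after they are started. It gives no reason for treating memantine differently, although its own background section ascribes the same kind of effect to both.

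At stake is how far this analysis can be read as a robustness check. If decliners in the placebo/40 mg arm started memantine more often and it helped them, the retained data would narrow the difference, and the check would not show it.

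**Working it through.** **1. Does the rule cover memantine under another name?** No. The text and Table 6 agree on AChEIs, Table 6 expands the term, and Section 4.1.1 places memantine in a different class. This is not an inconsistency between text and table.

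**2. The relevant places side by side**

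| Place | AChEI | Memantine |
|---|---|---|
| 4.1.1, effect | symptomatic only | symptomatic only |
| 5.3.2, may be started in the extension | yes | yes |
| 8.2.12, screening subgroup | pooled with memantine | pooled with AChEI |
| 8.2.7.1, primary model | screening use is a covariate | no term |
| 8.2.7.1 and Table 6, second supportive analysis | data after start excluded | data after start kept |

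**3. Does the initiation trigger matter in the extension?** Yes.

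- Sections 5.6 and 7.1.4.1 say that subjects who permanently stop study drug leave the trial, and Section 5.8 ends the retrieved-dropout approach. Section 8.2.4.1 admits extension observations only from subjects dosed within 28 days on each side of the Week 104 visit. After Week 104 there is little for the discontinuation trigger to remove, so the concomitant-drug trigger does most of the work.
- A subject already on an AChEI at screening has no first AChEI start left to trigger the rule. Adding memantine is the remaining new start, and it is not caught.
- Section 4.2.1.2 lets subjects who progress to dementia during the extension continue, so such subjects can contribute Week 130 data.

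**4. Size.** The plan states no figure to reproduce, and the documents give no memantine start rate or effect on CDR-SB. A simple expression for what is left in the difference is:

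bias = (between-arm difference in the proportion with retained post-memantine data at Week 130) × (effect of memantine on CDR-SB)

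Assumed inputs, not from the documents: a gap of 2 to 10 percentage points and an effect of 0.25 to 1.0 point.

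- Low end: 0.02 × 0.25 = 0.005 point
- High end: 0.10 × 1.0 = 0.10 point

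Only subjects who start memantine with no earlier post-baseline AChEI initiation count towards the gap. The others are already excluded from the AChEI start onwards.

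**5. Scale.** Section 8.2.11.1 gives no Week 130 treatment difference, and Table 9 came from simulation, so a reference value has to be back-solved from its 73.9% marginal power:

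- n per arm = 450 × (1 − 0.37) = 283.5
- baseline-adjusted SD from Table 8 = 3.05 × √(1 − 0.359²) = 2.847
- SE = 2.847 × √(2/283.5) = 0.239
- difference = (2.242 + 0.640) × 0.239 = 0.69 point, using two-sided α = 0.02495

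With the SD of change (2.856) the result is again 0.69; with the unadjusted SD (3.05) it is 0.74. Against 0.689, the illustrative bias is 0.005/0.689 = 0.7% to 0.10/0.689 = 14.5%. The width of that range reflects how little is known. It is not an estimate.

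**The case against.** The strongest reply is that the plan never says this analysis removes symptomatic-drug effects. It speaks of off-regimen data, and Table 6 labels the analysis by exactly what it excludes. That stands as far as it goes: the symptomatic-drug purpose is an inference. But AChEI initiation is the only concomitant-drug trigger, and the property that would explain it in these documents, the one in Section 4.1.1, is shared by memantine.

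The subgroup in Section 8.2.12 concerns use at screening, and the primary and Cox models use AChEI alone, so the rule matches the modelling convention. This weakens the subgroup as evidence but supplies no reason to leave memantine out.

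Excluding more data also has a price: the subjects removed may be faster decliners, and their Week 130 values would then rest on the missing-at-random assumption. That is true, but the plan already accepts the same price for AChEI starters.

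A reader might infer four stronger things that the documents do not support:

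- **That the result would be presented as free of symptomatic-drug confounding.** No section says so.
- **That the problem grows at later visits.** The analysis covers only the primary endpoint at Week 130, and Section 8.2.7.2 rules out sensitivity analyses of exploratory endpoints.
- **That memantine starts are mishandled over all 130 weeks.** Section 2.1 places the initial 104-week trial in a separate amendment, so its concomitant-drug rules are not visible here. Section 5.1.3 also excludes subjects who had progressed to AD dementia by investigator diagnosis in that period, which removes many of the fastest decliners.
- **That the primary result or type I error is compromised.** There are no formal hypotheses (Sections 8.1.1 and 8.2.10), and this is one of three supportive analyses.

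**Conclusion.** The point holds as a limited gap. The second supportive analysis removes data after one class of newly started symptomatic treatment and keeps data after the other class that the protocol names and allows to be started. It is therefore only a partial check on the delayed-start comparison at Week 130.

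The size is unknown. The illustrative 0.005 to 0.10 point rests wholly on assumed start rates and an assumed effect. The direction, a narrower difference, further assumes more memantine starts in the placebo/40 mg arm and a beneficial effect on CDR-SB. A bias in that direction would work against MK-8931 and would not create false support for disease modification. The gap is shown for Weeks 104 to 130 only. It affects how robustness is interpreted and leaves the primary analysis as planned. It is a cheap improvement of low severity.

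**What to change.** In Section 8.2.7.1 (the introduction to the supportive analyses and the paragraph on the second one) and in the matching row of Table 6, define the analysis as excluding observations after permanent study-drug discontinuation or after initiation of an AChEI or memantine, whichever is first. Make the change before the sponsor is unblinded at the end of the initial 104-week trial, so that it is not a post hoc choice.

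No new data collection is needed in the extension: the flow chart in Section 6.0 records concomitant medication at every scheduled visit, the same source the AChEI rule uses. The cost is fewer late observations. Between Weeks 104 and 130 the only scheduled CDR is the one at Week 130, so a subject who starts memantine in that interval loses that assessment. The loss may be uneven by arm, and this one supportive analysis will lean more on missing at random. Reporting the number of observations excluded by arm and by trigger would let a reader judge that cost.
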